3) Consent will be obtained via mail. Alternatively, participants have the option of receiving the informed consent in hard-copy via mail. The research team will mail 2 consent forms to the participant. The consent discussion will be conducted over the phone before the participant signs the forms. Members of the research team will be available to answer questions or explain any details further. The participant will be instructed to sign both, keep one for their records, and mail back the second using the self-addressed stamped envelope included in the mailing. Informed consent will be obtained prior to proceeding with any study procedures.

**TREATMENT.** All participants will receive the Supportive Parenting of Anxious Childhood Emotions (SPACE) intervention, a parenting intervention based on a cognitive-behavioral approach to anxiety. In SPACE, parents learn to support their children through instilling a message of support and encouragement; that they acknowledge their child's difficult experience with anxiety while conveying confidence that they can cope with stressful situations. This is done through specifically identifying parental accommodation behaviors they currently use and steadily reducing engagement in those behaviors. In the therapist-led SPACE group, therapists will follow the SPACE treatment manual, "Treating Childhood and

Adolescent Anxiety." In the low therapist contact bibliotherapy SPACE group, treatment will be provided using "Breaking Free of Child Anxiety and OCD," which is a parent-oriented book adaptation of the SPACE program for child and adolescent anxiety and/or OCD.

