## Section G: Sample Size/Data Analysis

### G1. Sample Size

How many subjects (or specimens, or charts) will be used in this study?

Local: 240      Worldwide: 240

Please indicate why you chose the sample size proposed:

We will enroll 120 parent-child dyads (n = 240 total children and parents), we anticipate 90 dyads will be eligible (n = 180), in order to meet an intent-to-treat sample size of 45 parent-child dyads per group, accounting for screen-fail rates. This exceeds our anticipated needs of 34 parent-child dyads per group to detect statistical significance in response rates on the CGI-I, the primary outcome measure. The power analysis assumed  $\alpha = .05$ , power = .95, as well as a 24% response rate for the parent self-guided intervention (based on our previous work with a similar approach; Storch et al., under review) and a 66% response rate for individual SPACE based on the Lebowitz et al. (2020) trial. We also anticipate the target sample size will be more than enough to detect differences in reductions on the Pediatric Anxiety Rating Scale (PARS), our other primary outcome, based on the Lebowitz et al. (2020) trial and our own preliminary analysis (Storch et al., under review). For this outcome, we anticipate needing 16 participants to detect statistically significant differences. This assumes an effect size of  $f = .845$ ,  $\alpha = .05$ , power = .95, and a correlation among repeated measures of  $r = .33$ .

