### G2. Data Analysis

Provide a description of your plan for data analysis. State the types of comparisons you plan (e.g. comparison of means, comparison of proportions, regressions, analysis of variance). Which is the PRIMARY comparison/analysis? How will the analyses proposed relate to the primary purposes of your study?

Descriptive statistics on all randomized participants will be analyzed and if any key variables (e.g. anxiety severity) differ across groups, they will be controlled for in analytic models via inclusion as a covariate. Violations of distributional assumptions will be addressed (e.g. robust sandwich estimators and interval smoothing for continuous variables, and exact logistic regression) in the case of sparingly distributed dichotomous dependent variables.

Study Aims 1-4 address pre-post group differences as a result of treatment, statistical moderation of pre-post treatment effects, and evaluation of additional observed change from post-treatment to 1-month follow up. Chi-square analyses will compare dichotomous outcomes (i.e., treatment response rates). Mixed within-between (time by treatment group) analysis of covariance (ANCOVA) will be used to assess pre-post and post-1-month follow up changes in continuous outcomes (i.e., symptom severity). Within-group change on continuous measures from post-treatment to 1-month follow up will be assessed by dependent t-tests for each treatment group. Between group differences in study dropout will be assessed by logistic regression.

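### G2 does not fix baseline PARS as a covariate, which costs about a third of the information at G1's r = .33 with equal SDs, and G1's figure of 16 does not match the test G2 plans

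*Combined protocol and SAP*

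**What the plan says.** Section G1 bases the sample size on CGI-I response, with "a 24% response rate for the parent self-guided intervention" against 66% for standard SPACE. This gives 34 dyads per group. It plans 90 eligible dyads "in order to meet an intent-to-treat sample size of 45 parent-child dyads per group, accounting for screen-fail rates".

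For PARS, G1 calls this sample "more than enough to detect differences in reductions on the Pediatric Anxiety Rating Scale (PARS), our other primary outcome". It then states: "For this outcome, we anticipate needing 16 participants to detect statistically significant differences". The inputs are f = .845, α = .05, power .95 and "a correlation among repeated measures of" r = .33. G1 does not name the test, and does not say whether 16 is a total or per group.

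Section G2 gives the analysis: "Mixed within-between (time by treatment group) analysis of covariance (ANCOVA) will be used to assess pre-post" and post-treatment to one-month changes in continuous outcomes. On covariates its only rule is that "if any key variables (e.g. anxiety severity) differ across groups, they will be controlled for in analytic models via inclusion as a covariate". It gives no criterion for a difference and names no covariate that is always included.

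**The concern.** Two things do not fit together.

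First, the model for a primary outcome is left open until the data are seen. Baseline PARS is collected on everyone, but the stated rule brings anxiety severity in only after an observed imbalance. At a modest pre-post correlation such as .33, an unadjusted time-by-group test is inefficient, because subtracting a weakly correlated baseline adds noise.

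Second, the figure of 16 suggests so much spare power for PARS that the choice of analysis hardly matters. That depends on a very large effect between two arms that share one programme (F2: "All participants will receive the Supportive Parenting of Anxious Childhood Emotions (SPACE) intervention"). If the effect is smaller than f = .845 implies, the analysis decides how much the 90 dyads can show.

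**Working it through.** **Inputs.** From G1: f = .845, α = .05, power .95, r = .33, response 24% and 66%, 45 per arm. From G2: a pre-post test, so m = 2 time points. Assumed: equal pre and post SDs unless stated, and SD units of a single PARS measurement.

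**1. Reproducing 16** (noncentral F, two groups, N in total).
- Between-groups main effect: λ = f²Nm/(1+(m−1)r). At N = 16, λ = 0.714 × 32/1.33 = 17.2 on 1 and 14 df, power .970. At N = 14, power is .944. The smallest even N is therefore 16, in total.
- Time-by-group: λ = f²Nm/(1−r). At N = 10, λ = 0.714 × 20/0.67 = 21.3 on 1 and 8 df, power .980. At N = 8, power is .927. The answer is 10.
- One other route also gives 16: a three-time-point interaction with the correlation already absorbed in f. It is not the two-time-point comparison in G2, and it would make no use of the r that G1 quotes.

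**2. The gap that f = .845 implies.**
- Read as a post-treatment-only comparison, the most lenient reading: 2f = 1.69 SD.
- In the test that reproduces 16, 2f is the gap averaged over baseline and post-treatment. Randomisation makes the expected baseline gap zero, so the post-treatment gap must be 4f = 3.38 SD.

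**3. What G1's response rates suggest** (one latent scale behind CGI-I and PARS, an assumption).
- Logit: ln[(.66/.34)/(.24/.76)] = 1.816, and 1.816 × √3/π = 1.00 SD.
- Probit: 0.412 − (−0.706) = 1.12 SD.
- Sections C and I give 88% response for SPACE. Using 88% in place of 66%, the same conversions give 1.73 and 1.88 SD.

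**4. Dyads needed at 1.00 to 1.12 SD, 95% power.**
- Time-by-group: 36 to 29 per arm (72 to 58 in total).
- Adjusted for baseline PARS: 25 to 20 per arm (50 to 40 in total).

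**5. Efficiency.** With two time points and no covariate, time-by-group is a t-test on change.
- Variance of change: 2(1−r) = 1.34 SD².
- Variance adjusted for baseline: 1−r² = 0.891 SD².
- Ratio: 0.891/1.34 = 0.665, a loss of 33.5%. Unadjusted, 45 per arm carries the information of 45 × 0.665 = 29.9 per arm adjusted.
- With post/pre SD ratio k, the loss is 1 − k²(1−r²)/(1+k²−2rk): 49% at k = 0.8, 20% at 1.25, 11% at 1.5.

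**6. Power at 45 per arm, complete data, unadjusted and adjusted.**

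| Post-treatment gap | Time-by-group | Adjusted |
|---|---|---|
| 0.6 SD (assumed) | 68% | 85% |
| 0.7 SD (assumed) | 81% | 94% |
| 1.0 SD | 98% | 99.9% |

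If 34 per arm have outcome data (assumed), power at 1.0 SD is 94% unadjusted and 99% adjusted.

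**The case against.** The strongest reply is that G1's working conclusion survives. CGI-I sets the sample size, and 45 per arm is ample for PARS at the gap that G1's own rates suggest. That stands. A reader might infer from the figure of 16 that the trial is underpowered for PARS. The documents do not support that at G1's assumed effect.

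The response-rate benchmark is also open to challenge. It crosses from one outcome to another, while G1 bases the PARS effect on the cited SPACE trial and on preliminary data that the documents do not show. CGI-I rates improvement, so its latent gap may be in change-score units. Time-by-group would then need 54 to 44 dyads in total, still well above 16. With 88% in place of 66%, the benchmark rises enough to cover 1.69 SD, though not 3.38 SD. So G1's rates do not refute the lenient reading outright.

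G2 does say ANCOVA, which may be meant to include a baseline covariate. That is a fair reading, but the only covariate rule written down is conditional.

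The one-third loss needs equal SDs. The entry threshold of 12 on PARS (F1) truncates baseline scores, so a larger post-treatment SD is plausible, and the loss would then be smaller.

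Two further readings should be resisted. One is that .845 is a mislabelled d: G1 prints f, and f = .845 reproduces 16. The other is that omitting the covariate biases the result. Under randomisation, chance imbalance is part of the variance already counted in step 5, not a second harm.

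**Conclusion.** The point holds as one of avoidable inefficiency and an unsupported figure.

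- **Analysis.** G2 fixes no baseline covariate for a primary outcome and leaves the model to be chosen from the data. If the covariate is not included, the loss is about one third at r = .33 with equal SDs, and 11% to 49% over the SD ratios examined. In practice it matters for gaps below about 1 SD, or if dropout is appreciable. G1's sizing allows explicitly for screen failure only, although 45 exceeds the 34 needed for CGI-I.
- **Sample-size statement.** The 16 matches a main effect averaged over two time points, not G2's pre-post time-by-group test. In that test it implies a gap of about 3.4 SD, which neither 66% nor 88% response supports under the conversion used here. The test behind 16 is inferred from the match, since G1 does not name it.

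The size of the trial needs no change.

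**What to change.** Keep 45 per arm.

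- **G2:** before data are seen, specify the primary PARS analysis as post-treatment PARS compared between arms, with baseline PARS always a covariate whatever the observed baseline difference. A model that constrains the baseline means to be equal would serve as well. Make time-by-group secondary.
- **G1:** replace the sentence on 16 participants with what the sample can detect under that analysis at r = .33. With 45 per arm this is about 0.56 SD at 80% power and 0.73 SD at 95%. If 34 per arm have outcome data (an assumption), it is 0.65 and 0.84 SD.

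The cost is one sentence in each section. No extra participants, visits or measures are needed, because baseline PARS is already collected. The plan gives up only the reassurance of the 16.

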### G2. Data Analysis

Provide a description of your plan for data analysis. State the types of comparisons you plan (e.g. comparison of means, comparison of proportions, regressions, analysis of variance). Which is the PRIMARY comparison/analysis? How will the analyses proposed relate to the primary purposes of your study?

Descriptive statistics on all randomized participants will be analyzed and if any key variables (e.g. anxiety severity) differ across groups, they will be controlled for in analytic models via inclusion as a covariate. Violations of distributional assumptions will be addressed (e.g. robust sandwich estimators and interval smoothing for continuous variables, and exact logistic regression) in the case of sparingly distributed dichotomous dependent variables.

Study Aims 1-4 address pre-post group differences as a result of treatment, statistical moderation of pre-post treatment effects, and evaluation of additional observed change from post-treatment to 1-month follow up. Chi-square analyses will compare dichotomous outcomes (i.e., treatment response rates). Mixed within-between (time by treatment group) analysis of covariance (ANCOVA) will be used to assess pre-post and post-1-month follow up changes in continuous outcomes (i.e., symptom severity). Within-group change on continuous measures from post-treatment to 1-month follow up will be assessed by dependent t-tests for each treatment group. Between group differences in study dropout will be assessed by logistic regression.

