## **Section F: Design/Procedure**

### **F1. Design**

Select one category that most adequately describes your research:

c) Pilot

Discuss the research design including but not limited to such issues as: probability of group assignment, potential for subject to be randomized to placebo group, use of control subjects, etc.

A total of 120 children-parent dyads will participate and will be randomized in a 1:1 ratio into one of two groups: (1) the standard SPACE group and 2) the bibliotherapy, low therapist contact SPACE group.

Inclusion Criteria:

- 1) The child is between the ages of 7 to 17 at enrollment
- 2) The child has clinically significant symptoms of anxiety and/or OCD, as indicated by a score of 12 or higher on the Pediatric Anxiety Rating Scale (PARS).
- 3) The child is appropriate for anxiety-focused treatment (e.g., anxiety is the primary problem as diagnosed using the Kiddie Schedule for Affective Disorder and Schizophrenia (K-SADS), and if secondary psychopathology is present it will not interfere with treatment).
- 4) One parent/guardian is able and willing to participate in assessment and treatment (e.g., has sufficient English fluency, the decisional capacity to participate, and can commit to treatment duration).
- 5) The participating parent/guardian lives with their child at least 50% of the time.
- 6) Both parent and child are able to read and understand English.
- 7) The child has the intellectual and communication skills to engage in CBT, as judged by an experienced supervising clinician.
- 8) Participants must reside in Texas and parents must be in the state of Texas when taking calls.

Exclusion Criteria:

- 1) the child has a diagnosis of child lifetime bipolar disorder, drug or alcohol abuse, psychotic disorder, or conduct disorder.
- 2) the child has severe, current suicidal/homicidal ideation and/or self-injury requiring medical intervention (referrals will be made for appropriate clinical intervention).
- 3) the child is receiving concurrent evidence-based psychotherapy for anxiety, involving exposure therapy in at least 50%

of sessions.

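### Baseline PARS is adjusted for only if the arms happen to differ, by no stated criterion; fixing it as a covariate in advance would settle the model and usually tighten the PARS estimate

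*Combined protocol and SAP*

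**What the plan says.** G1 (Sample Size) names two primary outcomes: CGI-I response and "reductions on the Pediatric Anxiety Rating Scale (PARS), our other primary outcome". For PARS it assumes f = .845, α = .05, power .95 and "a correlation among repeated measures of" .33. It plans recruitment "in order to meet an intent-to-treat sample size of 45 parent-child dyads per group".

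G2 (Data Analysis) gives the model for continuous outcomes: "Mixed within-between (time by treatment group) analysis of covariance (ANCOVA) will be used to assess pre-post and post-1-month follow up changes in continuous outcomes". The label is ANCOVA, but no covariate is named. The only covariate rule in the document is conditional: "if any key variables (e.g. anxiety severity) differ across groups, they will be controlled for in analytic models via inclusion as a covariate". How a difference is to be judged is not stated, nor is how a triggered covariate enters the time-by-group model.

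F1 (Design) requires a PARS score of at least 12 at entry, so baseline PARS is available for every eligible child.

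**The concern.** Baseline severity is a sensible covariate, but the reason for adjusting is that it predicts outcome. Observed imbalance is the wrong trigger: in a 1:1 randomised trial any imbalance is chance, so the rule lets chance select the model for a primary outcome. Because the trigger is undefined, whoever decides what counts as a difference may do so after seeing the data.

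Two things follow.

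- **Trigger not met.** The time-by-group interaction over two time points is simply the between-arm difference in change. That carries avoidable noise unless the regression slope of post-treatment on baseline PARS is near 1.
- **Trigger met.** G2 leaves open what is then fitted. Baseline added only as a main effect does not alter the time-by-group estimate at all. Baseline with a time-by-baseline term gives the properly adjusted estimate.

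At stake are the width of the PARS interval, power if the true effect is well below the planned one, and a single PARS model fixed in advance.

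**Working it through.** **Inputs.** From G1: r = .33, 45 analysed per arm, f = .845. From F1: 1:1 allocation and the entry floor of 12. Assumed: k = baseline SD / post-treatment SD, since no PARS SDs are given. The entry floor makes k below 1 plausible, so k is run from 1 down to 0.5. No dropout is assumed.

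**The plan's own figures.** Response rates of 24% and 66% (two-sided .05, power .95, no continuity correction) give 34 per group, as stated. For PARS, the repeated-measures between-groups formula has λ = f²·N·2/(1 + r). It gives power .944 at N = 14 and .970 at N = 16, so the stated 16 also reproduces.

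**Formulas (post-treatment SD = 1).**
- Change-score variance ∝ 1 + k² − 2rk.
- Baseline-adjusted variance ∝ 1 − r² = 1 − .1089 = .891.
- Their difference is (k − r)², which is never negative.
- Conditional rule at level a, fully adjusted once triggered: (1 − r²) + (k − r)²·A, where A = 1 − a − 2cφ(c), c is the two-sided normal cut-off and φ the normal density. A is about .721 at a = .05 and .350 at a = .20.

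**Worked case, k = 1.** (k − r)² = .67² = .449. At a = .05 the rule's variance is .891 + .449 × .721 = 1.215, so always adjusting saves 1 − .891/1.215 = 26.6%. At a = .20 it is .891 + .449 × .350 = 1.048, a saving of 15.0%.

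**Variance reduction from always adjusting.** The last three columns are simulated at 45 per arm with 200,000 to 400,000 runs; repeat runs agree within a few tenths of a point.

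| k | Change-score variance | v never adjusting (large sample) | v rule, p < .05 | v rule, p < .10 | v rule, p < .20 |
|---|---|---|---|---|---|
| 1 | 1.340 | 33.5% | 26.2% | 21.7% | 14.8% |
| 0.8 | 1.112 | 19.9% | 14.7% | 11.8% | 7.7% |
| 0.7 | 1.028 | 13.3% | 9.3% | 7.4% | 4.7% |
| 0.6 | 0.964 | 7.6% | 4.7% | 3.7% | 2.3% |
| 0.5 | 0.920 | 3.1% | 1.4% | 1.1% | 0.7% |

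**Dependence on the unstated criterion.** The trigger fires in 5%, 10% or 20% of trials at those p-values. If it means a standardised difference above 0.10, it fires in about 64%, and the variance reduction shrinks to 1.3%, 0.4% and 0% at k = 1, 0.7 and 0.5.

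**Interval and power, 45 per arm.** The 95% CI half-width, in post-treatment SDs, is .397 when always adjusting. Under the rule (p < .05 to p < .20) it is .480 to .468 at k = 1, .423 to .419 at 0.7 and .401 at 0.5. For an illustrative 0.5 SD effect, which is not the plan's, power is 70% when always adjusting against 54% to 56%, 64% to 65% and 69%. F1 instead says "A total of 120 children-parent dyads will participate and will be randomized in a 1:1 ratio into one of two groups". At 60 per arm the percentage reductions are essentially the same, and that power is 82% against 66% to 69%, 77% to 78% and 81%.

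**How far the choice moves the estimate.** At 45 per arm the adjusted and change-score estimates differ by more than 0.10 post-treatment SD in 47% of trials at k = 1, 20% at 0.7 and 3% at 0.5.

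**How baseline enters.** In one simulated data set (k = 0.7) the time-by-group estimate was −0.0280 both without a covariate and with a baseline main effect (change-score SE 0.228). With a time-by-baseline term it was −0.0381 (SE 0.199), identical to regressing post-treatment PARS on arm and baseline.

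**What is not harmed.** Type I error under the p-value triggers is .034 to .050. At f = .845 and N = 90, power exceeds .999.

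**Cost of always adjusting.** Estimating the slope inflates variance by 1 + 1/(N − 4) = 1 + 1/86 = 1.012 at N = 90. It therefore loses only where (k − r)² < .891/86 = .0104. At r = .33 that means k between 0.23 and 0.43, and the loss is at most 1.2%.

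**The case against.** The strongest reply is that no planned conclusion changes. Type I error is safe, power at the planned effect is above .99, CGI-I is unaffected, the change contrast is valid under randomisation, and F1 classes the study as a pilot. All of that is correct. It limits the weight of the point without removing it, because the planned f is large and the unspecified model remains at any effect size.

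The size also depends on inputs the documents do not settle. 26% is the upper end, at k = 1, while the entry floor points to smaller k. The percentages assume full adjustment once triggered. The value r = .33 is a sample-size input, not a reported baseline-to-post PARS correlation. At r = .5 and 45 per arm the reduction against the rule (p < .05 to p < .20) is about 19% to 10% at k = 1 and 3% to 1.5% at 0.7. At k = 0.5 it becomes a loss of 0.9% to 0.4%. This stands: the precision gain ranges from substantial to nil or marginally negative.

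The ANCOVA label may mean that a fixed baseline covariate was intended, and G2 does not name PARS. But the only written route for a covariate is the conditional one, and its own example is anxiety severity. If fixed adjustment was intended, saying so resolves the point.

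**Conclusion.** The concern holds. The plan lets an undefined look at baseline imbalance decide whether its second primary outcome is adjusted for its own baseline, and it does not say what model results. At r = .33 and 45 per arm, always adjusting reduces variance against the p-value versions of the rule by 26% to 15% (k = 1), 9% to 5% (k = 0.7) or about 1% (k = 0.5). If the trigger is a standardised difference above 0.10, the reduction is 1.3% or less. These figures rest on assumed SD ratios, complete data and full adjustment once triggered. The case for pre-specification does not depend on any of them. The trial is not invalidated, but the change is worth making because it costs almost nothing.

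**What to change.** In G2, replace the conditional rule for PARS with wording such as: *Post-treatment PARS will be compared between arms in a linear model with treatment and baseline PARS, with baseline PARS included regardless of any observed baseline difference.*

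- Remove imbalance-triggered adjustment from the primary PARS analysis, or keep it as a sensitivity analysis with a stated criterion.
- Do not add baseline only as a main effect to the time-by-group model.
- A constrained longitudinal model with a common baseline mean is an alternative. It gives nearly the same result with complete data but can differ when outcomes are missing. Name one of the two as primary, and state how missing post-treatment PARS is handled.
- State separately which model serves the post-treatment to 1-month contrast, which the sentence above does not cover.
- Leave the chi-square test for CGI-I as it is.

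The cost is a few sentences in G2, the two decisions just listed (model and missing data) and one degree of freedom, about 1% of variance at N = 90. Baseline PARS is already collected for eligibility, so no visits, participants or measures are added.

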## Section D: Purpose and Objectives

The purpose of this study is to implement a parenting intervention based on a cognitive-behavioral approach to anxiety and OCD for children and adolescents aged 7-17. We will compare standard Supportive Parenting for Anxious Childhood Emotions (SPACE) to a low-contact, therapist-supported bibliotherapy version of SPACE using the book "Breaking Free of Child Anxiety and OCD."

Specifically, our aims are as follows:

1. To provide evidence of treatment efficacy for the full standard version of SPACE relative to a low therapist contact bibliotherapy version of SPACE (Lebowitz, 2020).
2. To determine pre-treatment predictors of treatment outcome, especially those that showed a moderate response to the low therapist contact bibliotherapy SPACE group compared to the standard SPACE group.
3. To compare treatment adherence between the standard SPACE group and the low therapist contact bibliotherapy SPACE group.
4. To explore treatment satisfaction, preferences, and feasibility of standard SPACE and low therapist contact bibliotherapy SPACE, overall and as a function of group status.

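### The covariate rule for imbalanced baselines has no specified method for CGI-I response, the primary outcome that sizes the trial, because the test named for it is a plain chi-square

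*Combined protocol and SAP*

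**What the plan says.** G1 bases the main sample-size calculation on the number of dyads needed "to detect statistical significance in response rates on the CGI-I, the primary outcome measure", and calls the PARS "our other primary outcome".

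G2 then assigns methods by type of outcome:

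- **Dichotomous outcomes:** "Chi-square analyses will compare dichotomous outcomes (i.e., treatment response rates").
- **Continuous outcomes:** a mixed time-by-group ANCOVA.
- **Dropout:** logistic regression.
- **Sparse dichotomous outcomes only:** exact logistic regression.

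G2 opens with a general rule. If key variables differ across the randomised groups, with anxiety severity as the example, "they will be controlled for in analytic models via inclusion as a covariate". The rule is not limited to continuous outcomes, and no threshold for a difference is given.

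**The concern.** The rule and the test do not fit together on the outcome that sizes the trial. A 2x2 chi-square compares two proportions and has no place for a covariate. The PARS model can carry one, but the CGI-I comparison as written cannot.

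If baseline severity turns out to be imbalanced, the sponsor has two options. It can report the unadjusted chi-square and depart from its own rule, or it can move to a model that the plan does not name, chosen once the data are visible. Because no threshold defines a difference, whether to adjust is also open at that stage. The choice of analysis for a primary outcome could then be challenged whatever the result.

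A smaller cost is that baseline PARS, which every randomised child has because it is an entry criterion (F1), goes unused in the CGI-I comparison.

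**Working it through.** **1. Reproduce the plan's figure.** Inputs from G1: 24% and 66% response, alpha .05, power .95. Equal allocation is in F1. Two-sided testing is assumed, since G1 does not state it. With a pooled rate of (.24 + .66)/2 = .45:

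n = [1.960·√(2·.45·.55) + 1.645·√(.24·.76 + .66·.34)]² / (.66 − .24)²
= (1.379 + 1.049)² / .1764 = 33.4, so 34 per group.

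This matches G1. It is an unadjusted two-proportion calculation, consistent with the chi-square.

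**2. Would the sparse-data route apply?** With 45 per arm, the anticipated responders are .24·45 = 10.8 and .66·45 = 29.7. The pooled expected counts per arm are .45·45 = 20.25 responders and .55·45 = 24.75 non-responders. The outcome is not sparse, so the exact logistic clause would not be triggered and the chi-square stands.

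**3. How likely is imbalance?** The SD of the difference in baseline means, in SD units, is √(2/45) = .211. A difference beyond 0.3 SD in either direction is 0.3/.211 = 1.42 standard errors, with probability about 15%.

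**4. What does imbalance do to the unadjusted difference?** Assume that response is a cut on a latent normal variable correlated r with baseline. The documents give no such r. G1's .33 is a correlation among repeated PARS measures and is borrowed here; .5 is a stronger illustrative value. In an arm with response rate p, the average change in response per SD of baseline is r·φ(Φ⁻¹(p)). The shift in the risk difference per SD of imbalance is the mean of the two arms' slopes.

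| Rates | r = .33 | r = .5 |
|---|---|---|
| 24% v 66% | (.103 + .121)/2 = .112 | (.155 + .183)/2 = .169 |
| 45% v 45% | .131 | .198 |

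Simulation of trials with 45 per arm gives .114 to .133 and .173 to .185 unadjusted, and at most .018 adjusted. Overall the shift is about 10 to 20 points per SD against 2 or less. An imbalance of 0.3 SD therefore moves the unadjusted difference by about 3 to 6 points.

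**5. Precision.** The share of variance explained is the sum of squared slopes over the sum of p(1 − p). At 24% v 66% this is 6.2% for r = .33 and 14.2% for r = .5. Simulated ratios of unadjusted to adjusted variance are about 1.04 to 1.18. At r = .1 the share is 0.6%, which is less than the cost of estimating one more coefficient (about 1/87 = 1.1%), so nothing is gained.

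**6. Power at 45 per arm.**

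- *Planned 24% v 66%:* the chi-square has Φ[(.42·√45 − 1.379)/.638] = 98.8% by formula and 98.5% by exact enumeration. Simulated gains at r = .33 to .5 are about 1 point or less.
- *Assumed 40% v 66%* (40% is not in the documents): chi-square power is about .69 to .70. The adjusted standardised difference gives .74 at r = .33 and .79 at r = .5. Part of this is a slightly more liberal test, because a covariate unrelated to outcome still moved power from .70 to .72.

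**7. False positives given imbalance.** With no treatment effect, 45% response in both arms and an imbalance of 0.42 SD (roughly the p = .05 level at this size), the chi-square rejects 9.7% of the time if the covariate log-odds ratio is 1.0 per SD, against 5.9% adjusted. At a log-odds ratio of 0.5 the figures are 5.9% and 5.6%.

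**The case against.** An unadjusted chi-square is valid under randomisation and matches the sample-size calculation, so always adjusting could be called a preference. This stands as far as overall error control goes. It does not remove the conflict, because the plan itself commits to adjusting when groups differ.

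The covariate rule can also be read as calling for a model whenever imbalance arises, and G2 shows that logistic models are within the sponsor's repertoire. That is fair. Adjustment of CGI-I response is therefore unspecified, not barred, and a claim that it cannot be done would go too far.

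A reader might infer that Aim 2 cannot be carried out. The documents do not support that. Section D says only "To determine pre-treatment predictors of treatment outcome" and does not name CGI-I. G2 speaks of moderating pre-post effects, which the ANCOVA on PARS can carry. No section promises moderation on CGI-I response.

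A reader might also infer a serious loss of power. At the planned rates there is almost none. The larger gains need a smaller true effect that the documents do not contemplate, and part of them reflects the size of the test. The size of the benefit depends throughout on an assumed correlation.

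**Conclusion.** The point holds as an internal inconsistency on a primary outcome. G2's covariate rule has no stated method for a non-sparse CGI-I response, which leaves the choice of model until after the data are seen. This rests on the text and not on the simulations.

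Its numerical importance is modest and conditional. If baseline severity is a fair predictor of response, an imbalance of a size expected in about one trial in seven would shift the unadjusted difference by several points. If it is a weak predictor, neither the shift nor the precision gain amounts to much. The planned sample size is unaffected. The change should be made because it settles the analysis in advance at little cost, not because the planned test is invalid or underpowered.

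**What to change.** In G2, make the CGI-I response comparison a logistic regression on treatment group and baseline PARS, fitted whether or not the groups differ at baseline. Report the covariate-standardised difference in response proportions with a robust 95% CI and the matching test. Keep the chi-square as a supporting unadjusted analysis. Reword the imbalance rule so that observed imbalance no longer decides the primary model.

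If a group-by-baseline term is added for CGI-I response, label it exploratory. At 45 per arm its power is only about 27% for an interaction log-odds ratio of 0.7 per SD and 49% for 1.0, both assumed effect sizes.

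The cost is a few sentences in G2 and slightly more analysis work. No new data and no change in sample size are needed. The adjusted test is marginally more liberal at this size: simulated null rejection is about .05 to .057, against .041 to .047 for the chi-square.
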